2. INTRODUCTION

DGATs catalyze the terminal step in TG synthesis, specifically the esterification of a fatty acid with DAG, resulting in the formation of TG.¹ In mammals, 2 structurally unrelated DGAT enzymes (DGAT1 and DGAT2) have been characterized. DGAT1 is highly expressed in the intestine and plays a central role in fat absorption² whereas DGAT2 is highly expressed in liver and adipose.³ DGAT2i is postulated to decrease hepatic TG synthesis and hepatic lipid burden in NAFLD and NASH. Based on observations in nonclinical studies conducted, it is hypothesized that DGAT2i will impact both physiological drivers contributing to NASH via direct inhibition of liver TG synthesis, as well as adaptive responses leading to reduction in hepatic DNL.

PF-07202954 is a potent and selective, orally administered, DGAT2i demonstrating greater than 4500-fold selectivity over related acyltransferases. It is being developed for the treatment of NASH with liver fibrosis.

2.1. Study Rationale

The current clinical study is the first one proposed with PF-07202954. It is designed as a 3-part study in healthy adults. Part 1 will evaluate the safety, tolerability, and plasma PK of PF-07202954 with administration of escalating, single, oral doses of PF-07202954 with a standard morning meal. Part 2 will evaluate safety, tolerability, and plasma and urine PK as well as markers of clinical activity, in adults with simple hepatic steatosis, upon repeated, escalating doses of PF-07202954 administered once daily with a standard morning meal for 14 days. Based on observed data from Part 1 and Part 2, assessment of the effect of a high-fat/high-caloric meal versus a fasted state on the plasma PK of PF-07202954 may be conducted in Part 3.

2.2. Background

The World Gastroenterology Organization has indicated that NAFLD and NASH are now the number one cause of liver disease in Western countries as the prevalence of NAFLD has doubled during last 20 years, while the prevalence of other chronic liver diseases has remained stable or even decreased.⁴ NASH is diagnosed clinically by liver biopsy demonstrating steatosis, inflammation, and cytological ballooning of liver hepatocytes, often with varying degrees of fibrosis. NASH progresses with increasing severity of fibrosis, with cirrhosis developing in a subset of patients⁵ and a common complication of cirrhosis being HCC.⁶ NASH is a subset of NAFLD (defined as presence of $\geq 5\%$ hepatic steatosis in the absence of other liver disease etiologies) that is associated with increased all-cause mortality, cirrhosis and end-stage liver disease, increased cardiovascular mortality, and increased incidence of both liver-related and non-liver related cancers.⁷

In a meta-analysis, the global prevalence of NAFLD was estimated at 25%, with the prevalence of NASH in the subset with biopsy-proven NAFLD assessed at 59%.⁵ The majority of the population with NAFLD has simple steatosis which has, in general, a benign clinical course. A proportion of participants with NAFLD progress to having hepatocellular ballooning and lobular inflammation, taking close to a decade to progress from 1 stage to the

next and 30-40 years to develop cirrhosis; however, a smaller subset of participants progress very rapidly (within 10 years) to liver cirrhosis from NAFLD.⁷ Patients with NASH may be asymptomatic or have non-specific symptoms such as fatigue, despite having significant disease on liver biopsy and associated risk for progression to cirrhosis and liver-related mortality. The 5-year (67%) and 10-year (38%) survival rates in patients with NASH is significantly different than in those with NAFLD. The pooled liver-specific and overall mortality incidence rate estimates among those with NAFLD were calculated at 0.8 and 15.4, respectively, per 1,000 person-years. In contrast, amongst the population with NASH, the incidence rate estimates were 11.8 (liver-specific) and 25.6 (overall) mortality.⁷

Elevated rates of hepatic DNL have been reported to be a distinctive characteristic of NAFLD.⁸ Clinically, those with elevated liver fat showed a more than 3-fold increase in the rate of hepatic DNL relative to participants with normal liver fat, but no differences between the groups were detected in adipose FFA flux or in production of VLDL from FFAs. Consequently, when comparing the absolute sources of FA incorporated into VLDL-TG, elevated hepatic DNL was the only source significantly increased in participants with high liver fat.⁸ Hepatic DGAT2 deficiency reduces diet-induced hepatic steatosis without increasing inflammation or fibrosis in mice.⁹ This supports development of DGAT2 inhibitors as a therapeutic strategy for treating NASH with liver fibrosis and preventing downstream consequences.

2.2.1. Nonclinical Pharmacology

PF-07202954 is a potent and selective inhibitor of hDGAT2. By in vitro biochemical assessment of hDGAT2, PF-07202954 inhibits hDGAT2 with an IC₅₀ of 10.1 nM. The selectivity of PF-07202954 for DGAT2 was supported by in vitro studies demonstrating >4500-fold selectivity by biochemical assessment versus related acyltransferases including recombinant hDGAT1, hMGAT2, and hMGAT3, as well as mouse MGAT1. In primary cultures of human hepatocytes, PF-07202954 exhibits an IC₅₀ of 11.4 nM for inhibition of hDGAT2. PF-07202954 also inhibits DGAT2 within rat and nonhuman primate primary hepatocytes, yielding IC₅₀ of 114 nM and 35.4 nM, respectively.

In vivo, following single dose administration, PF-07202954 demonstrates robust, dose- dependent reduction of plasma and hepatic triacylglycerol in rats fed a sucrose diet. In longer term studies in Western diet fed rats, PF-07202954 also reduces both plasma triacylglycerol and hepatic lipid accumulation. In line with the proposed mechanism of action, PF-07202954 dosing in both sucrose and Western diet fed rats results in suppression of key genes involved in hepatic lipid metabolism, including mRNA expression of Pcsk9. In these nonclinical models dosed with PF-07202954, Pcsk9 mRNA was decreased relative to vehicle treated animals by 64% and 75% in the Western and sucrose diet models, respectively.

2.2.2. Nonclinical PK and Metabolism

Single-dose PK studies with PF-07202954 were conducted after IV administration in rats, dogs, and monkeys and oral administration in rats and monkeys. PF-07202954 demonstrates incomplete oral absorption with mean F of 4% in rats and 21% in monkeys. PF-07202954 exhibited moderate to high CL_{plasma} and moderate V_{ss} in rats, dogs, and monkeys, resulting in a short terminal elimination $t_{1/2}$ of ≤ 1.5 hours. Systemic exposure of PF-07202954 as measured by C_{max} and AUC_{24} in repeat oral dose toxicity studies increased with increasing dose in rats and monkeys with evidence of some accumulation in both species. Systemic exposure of PF-07202954 was higher in female rats than in male rats, where sex-related differences were not observed in monkeys. In vitro, PF-07202954 showed moderate passive permeability and preliminary studies indicated that PF-07202954 was a substrate for MDR1 (also known as P-gp) and BCRP efflux transporters.

Following IV administration of PF-07202954, the percent of PF-07202954 dose recovered unchanged in urine was 12% (rat), 25% (dogs), and 2.0% (monkeys). The renal clearance estimates exceed GFR by ~2-fold indicating a net active renal elimination process in rats and dogs but not in monkeys. PF-07202954 is a substrate for the human OAT3 but not OCT1 or OCT2. PF-07202954 was moderately bound to plasma proteins with f_u of PF-07202954 in plasma being 0.422 (rat), 0.531 (dog), 0.370 (monkey), and 0.382 (human). The blood-to-plasma ratios of PF-07202954 in rat, dog, monkey, and human suggest that PF-07202954 does not preferentially distribute into plasma versus red blood cells.

In vitro metabolite profiling in mouse, rat, rabbit, monkey, and human matrices and rat and monkey plasma, suggests that the primary metabolic clearance mechanism for PF-07202954 was oxidation with no unique human metabolites observed. Reaction phenotyping in human hepatocytes indicated CYP3A ($>87\%$) was primarily responsible for the oxidative metabolism of PF-07202954 with minor contributions from CYP2C9 and CYP2C19. However, in humans, metabolic CL of PF-07202954 is projected to account for approximately 40% of total CL, with the remaining 60% as renal CL. Modeling suggests a low risk of clinical DDI with PF-07202954 as a victim upon coadministration with CYP3A4 inhibitors or inducers. As OAT3 is predicted to contribute to the active renal secretion of PF-07202954 in humans, a potential risk of clinical DDI with PF-07202954 as a victim is anticipated upon coadministration with potent inhibitors of OAT3. At the projected effective human dose of 80 mg once daily, PF-07202954 has a low risk of eliciting DDI as a result of inhibition or induction of CYP enzymes or efflux and uptake transporters with the exception of direct inhibition of MATE1 and intestinal BCRP.

2.2.3. Biopharmaceutics

PF-07202954 is a weak base with pKa values of 7.5 and 2.5, thus exhibiting a strong pH-dependent change in solubility. It has high thermodynamic aqueous solubility at physiological pH. The solubility of PF-07202954 in simulated gastric fluid (pH 2.7) and unbuffered water (pH 8) is >27 mg/mL and 0.13 mg/mL, respectively. Solubility in simulated fasted and fed state intestinal fluids (pH 6.9 under both conditions) was observed to be 0.7 mg/mL and 1.2 mg/mL, respectively. Solubility of PF-07202954 is high relative to

the predicted clinical FIH dose range, thus the risk for solubility/dissolution-limited absorption and exposure-limiting precipitation is perceived to be low. Food is expected to have minimal impact on PF-07202954 PK – refer to [Section 4.2.5](#). Preliminary in vitro studies suggest PF-07202954 exhibits moderate in vitro permeability and is a substrate for the intestinal efflux transporters (P-gp and BCRP) that could potentially lead to non-linear plasma PK and high variability in exposure at lower doses.

2.2.4. Nonclinical Safety

PF-07202954 was evaluated in safety pharmacology studies, genetic toxicology studies, and repeat dose toxicity studies, of up to 6 weeks in duration, in rats and cynomolgus monkeys. Target organs in safety pharmacology and general toxicity studies included the CNS (convulsion), kidney/urinary system (degenerative/inflammatory process with evidence of altered renal function), and the CV system (increased QT and QTc-interval). Other key findings included nonadverse hematology changes and nonadverse findings in the gastrointestinal system. The highest NOEL for convulsion was 300 mg/kg which corresponded to total C_{max} of 39,000 ng/mL. The NOEL for QTc-interval changes was 30 mg/kg and corresponded to total C_{max} of 2770 ng/mL. The NOAEL in the 6-week pivotal toxicity studies were 300 mg/kg/day (in rats) and 100 mg/kg/day (in monkeys). In rats, the NOAEL corresponded to a total C_{max} of 6570 (in males) and 14,400 (in females) ng/mL and total AUC₂₄ of 36,800 (males) and 89,100 (females) ng•h/mL. In monkeys, the NOAEL corresponded to a total C_{max} of 14,500 ng/mL and total AUC₂₄ of 88,500 ng•h/mL.

PF-07202954 was not genotoxic. PF-07202954 may have potential risk for phototoxicity based on its UV absorption profile and will be evaluated for phototoxicity during exploratory development prior to enrollment in Phase 3 clinical studies. Further details of the nonclinical safety program are provided in the current IB.

2.3. Benefit/Risk Assessment

This study is the first time that PF-07202954 will be administered to humans. For healthy participants participating in this 3-part study, no clinical benefit is expected. The purpose of the study is to provide the basis for further clinical development of PF-07202954 as a potential new pharmacological agent for the treatment of participants with NASH with liver fibrosis. As of the issuance of this protocol, no specific human risks have been identified; potential risks based on nonclinical studies are summarized in [Table 1](#). The clinical impact of these potential risks will be minimized through the proposed cautious dose-escalation process wherein higher doses of both single- and repeated-oral doses of PF-07202954 will be administered only after lower doses have been found to be safe and well tolerated in this study and the a priori identified PK stopping limits will not be exceeded (refer to [Section 6.6.1](#)). In addition, this study includes standard, intensive inpatient monitoring of the participants following administration of single- and repeated-, escalating, oral doses of the study intervention.

More detailed information about the known and expected benefits and risks and reasonably expected adverse events of PF-07202954 may be found in the IB, which is the SRSD for this study.

2.3.1. Risk Assessment

Table 1. Potential Risks with PF-07202954 and C4171001 Design

Potential Risk of Clinical Significance	Summary of Data/ Rationale for Risk	Mitigation Strategy
Study Intervention – PF-07202954		
Decrease in renal function	
In a 6 week toxicity study in rats, renal tubular degenerative/inflammatory process with a pattern consistent with obstructive nephropathy - associated with evidence of altered renal function and lower urinary tract alterations without accompanying changes in SCr and BUN observed at the highest dose tested (1000 mg/kg/day) with most conservative total AUC₂₄ (in male rats) of 210000 ng•h/mL.	
Risk communicated through the IB;Heightened surveillance for potential case of acute kidney injury outlined in Section 7.1.2;PK stopping total AUC₂₄ criterion set at ≥200-fold lower exposures – refer to Section 6.6.1;Design features added including –
Enrollment limited to those with normal renal function as defined by eGFR cut-offs using CKD-EPI formulae, and normal UACR and UPCR – refer to exclusion criterion #7 in Section 5.2;Conduct of UACR, UPCR at all timepoints that urinalysis is undertaken following single and repeated dosingConduct of urine microscopy at all timepoints that urinalysis is undertaken following repeated dosing (in Part 2);CCI
Delayed cardiac repolarization	Increase QT and QTc observed in GLP CV study in monkeys at 14400 ng/mL (total C _{max}).	
Risk communicated through the IB;Serial assessment of triplicate, 12-lead ECGs following single- and repeated- doses of study intervention (Section 8.2.3) along with continuous telemetry following single doses (Section 8.2.3.1);PK stopping total C_{max} criterion set at close to 10-fold lower (1450 ng/mL) – refer to Section 6.6.1.
Convulsions	Convulsions noted in 1 monkey dosed 500 mg/kg/day where total C _{max} was 46000 ng/mL.	
Risk communicated through the IB;PK stopping total C_{max} criterion set at the conservative 1/10th exposure at NOAEL in 6 week GLP monkey study (1450 ng/mL) – refer to Section 6.6.1;As designed, participants will be under closely monitored environment for ≥72 hours post (last) dose.

PFIZER CONFIDENTIAL

Table 1. Potential Risks with PF-07202954 and C4171001 Design

Potential Risk of Clinical Significance	Summary of Data/ Rationale for Risk	Mitigation Strategy
Skin sensitivity to light; sunburn	Based on UV absorption profiles, PF-07202954 carries risk for phototoxicity.	Standard precaution as it relates to exposure to sunlight/high intensity UV light exposure including eye protection is proposed – refer to Section 5.3.3 .
Exposure in utero	To date, EFD studies with PF-07202954 have not been conducted: 
 And PF-07202954 is not mutagenic, clastogenic or aneuploidogenic in in vitro studies plus was negative in an in vivo rat micronucleus study. 	
 Risk communicated through the IB; Enrollment of WOCBP restricted to those using effective contraception – refer to Section 5.3.4 and Section 10.4: 
 As a measure of caution, serum pregnancy testing undertaken in all females. In males who are sexually active with a female partner of childbearing potential, use of barrier methods required/mandated – refer to Section 5.3.4 and Section 10.4.
DDIs resulting in change in exposure of background/concomitant medications	In vitro data indicate PF-07202954, at high doses, may be a CYP3A inducer.	
 Enrollment of WOCBP restricted to those using effective contraception (with restrictions on use of some hormonal methods) – refer to Section 5.3.4 and Section 10.4; CCl
	In vitro data indicate PF-07202954 is an inhibitor of MATE1, a renal transporter involved in tubular secretion of organic cations.	
 CCl
Study Procedures		
In Part 1 and Part 2, number of serial and parallel procedures carry risks for non-evaluative data	
 Planned safety and PK evaluation is standard for FIH studies in healthy participants; But addition of parallel, multiple, clinical activity parameters done to enable more robust exposure:response characterization. 	
 At selected timepoints where evaluation of safety, PK, and clinical activity is planned in parallel, doability of all procedures is preceded at sites selected for this study;

Table 1. Potential Risks with PF-07202954 and C4171001 Design

Potential Risk of Clinical Significance	Summary of Data/ Rationale for Risk	Mitigation Strategy

In Part 2, conduct of different imaging assessments of liver fat during study (ie, quantitative ultrasound-based FibroScan®) CCI
 
[REDACTED]
	
Procedures are relatively safe; potential risk for non-evaluable images include:
 
 • Too much motion, for example, due to increased anxiety, claustrophobia; • Ferric implants/devices, paramagnetic objects within/on body, ferric-containing tattoos in area of interest (abdomen, chest, arms); • Minimum duration of a priori fast not followed. 	
 • Permitting pre-procedure use of short-acting anxiolytics to manage anxiety CCI • Excluding participants if they have contraindications for MRI, or quantitative ultrasound-based assessments (FibroScan®); • Clear communication via ICD of preparation for each visit including duration of fast before procedures/visits.

In Part 1 and Part 2, dosing of study intervention with standard meal changes PF-07202954 exposure
	
In vitro data indicate that PF-07202954 has moderate passive permeability ($RRCK=2.9 \times 10^{-6}$ cm/sec), higher solubility at lower pH – refer to Section 2.2.3.
	
 • In Part 1 and Part 2, dosing with a standard (not high-fat/high-caloric) meal is proposed to permit assessment of clinical activity – CCI – refer to Section 4.2.5; • Dose range evaluated is envisioned to be adjusted based on observed plasma PK while following dose-escalation principles – refer to Section 6.6.1.
Other Factors Potentially Impacting Study Results		

In Part 2, baseline liver fat CCI too low hence potentially not permitting assessment of primary pharmacology (ie, liver fat reduction)
	
Population eligible is healthy with evidence of simple hepatic steatosis assessed using quantitative ultrasound at Screen.
	
In Part 2, study requires double-confirmation of assessment of liver fat (via CAP™ using FibroScan®) and lack of overt liver inflammation/fibrosis (via VCTE™ using FibroScan®) with eligibility required to be met prior to Baseline CCI;
 
 • CAP™ ≥ 270 dB/m when assessed on 2 different days permits $>90\%$ probability of liver fat being $\geq 6\%$ liver fat on baseline CCI; • VCTE <7.0 kPa when assessed on 2 different days being highly suggestive of lack of clinically significant inflammation/fibrosis.¹⁰

PFIZER CONFIDENTIAL

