4.3.2. Human Exposure Limits

Guided by the target organs of toxicity identified in the completed GLP, 6 week studies in rats and monkeys (refer to [Section 2.2.4](#), [Table 3](#) and [Table 4](#)), the PK exposure limits in this study are proposed as –

- **In Part 1 and Part 2: Total C_{max} : 1450 ng/mL** – reflecting the *conservative* 1/10th of the exposure at the NOAEL dose (100 mg/kg/day) in the 6 week toxicity study in monkeys [for the convulsions observed in 1 monkey in the exploratory toxicity study following PF-07202954 dose of 500 mg/kg/day];
- **In Part 1: Total AUC_{24} : 18,400 ng•h/mL** – reflecting 50% of exposure in males at the NOAEL dose (300 mg/kg/day) in the 6-week toxicity study in rats [for adverse renal findings];
- **In Part 2: Total AUC_{24} : 3,680 ng•h/mL** – reflecting 10% of exposure in males at the NOAEL dose (300 mg/kg/day) in the 6-week toxicity study in rats [for adverse renal findings] with revision to this stopping limit to be considered, via a protocol amendment post formal interim analysis, based on observed data in Part 1 *and* Part 2 in this study.

4.3.3. Rationale for Dose Selection in Part 1

The objective of Part 1 of this study is to explore the safety, tolerability, and plasma PK of PF-07202954 after administration of single escalating oral doses across a wide exposure range and potentially up to the maximum predefined human exposure limits ([Table 3](#)). Dosing will occur with a *standard* morning meal. The doses presented are projected based on nonclinical data and may be modified based on emerging human safety, tolerability, and PK data. Human PK parameter estimates, toxicokinetic data, and projected effective concentrations were used to establish the initial range of planned doses in this study. The projected human exposures are based on assuming dose-proportional increases in exposure within the planned dose range.

Table 3. Predicted Human Exposures at Proposed Single Doses of PF-07202954

Dose (mg)	Total Concentrations		Safety Margins ^{b,c}	
	C _{max} ^a (ng/mL)	AUC ₂₄ ^a (ng·h/mL)	C _{max} ^b	AUC ₂₄ ^c
10	10	180	140	102
30	31	540	46	34
100	100	1800	14	10
300	310	5400	4.6	3.4
600	620	11,000	2.3	1.7
1000 ^d	1040	18,000	1.4	1.0 ^d

- a. C_{max} and AUC₂₄ were estimated using projected human PK parameters for PF-07202954 using CL_{plasma}=3.34 mL/min/kg; V_{ss}=2.3 L/kg; F=0.32; ka=0.2 h⁻¹; human fu=0.382; body weight=70 kg.

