- If, at any dose level, the average exposure reaches or exceeds the PK stopping limits defined as the following:
 - total C_{max} =1450 ng/mL (in Part 1 and Part 2);
 - total AUC_{24} =18,400 ng•h/mL (in Part 1);
 - total AUC_{24} =3,680 ng•h/mL (in Part 2 with revision to this stopping limit to be considered, via a protocol amendment post formal interim analysis, based on observed data in Part 1 *and* Part 2 in this study).
- If, based on the observed data, the group mean C_{max} or AUC (based on total plasma concentration) of the next planned dose is projected to exceed the escalation limits, that dose will not be explored. Modified doses may be explored if they are not expected to exceed PK stopping criteria.

Progression to the next dose level will occur if the last dose was well tolerated and after satisfactory review of the available safety and PK data.

- **Part 1:** A minimum of 6 participants (including at least 1 participant who received placebo) of the planned 8 participants to be dosed at each dose level must complete dosing and planned assessment to a minimum of 24 hours post dose. Safety, tolerability, and plasma PK data through ***at least 24 hours post dose*** for the prior dose level (along with cumulative data from all previously administered doses) will be reviewed in order to identify the next dose-level to escalate to in the next period.
- **Part 2:** A minimum of 8 participants (including at least 1 participant who received placebo) of the planned 10 participants to be dosed at each dose level must complete the planned 14 days of dosing and planned safety/tolerability assessments to a ***minimum of 24 hours post dose on Day 14***.
 - In addition, plasma PK data through ***at least 24 hours post dose on Day 7 (or*** at least 24 hours post dose on Day 14 ***if*** the observed $t_{1/2}$ of PF-07202954 in Part 1 is greater than 30 hours) for the prior dose level (along with cumulative data from all previously administered doses) will be reviewed in order to identify the next dose-level to escalate to in the next period.

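### Table 1 credits the AUC24 stopping criterion with a renal margin of at least 200-fold; the limits in force give about 11-fold in Part 1 and 57-fold in Part 2

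*Protocol*

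**What the plan says.** Section 2.2.4 lists the kidney and urinary system among the target organs. In the renal row of Table 1, the rationale column describes tubular findings at the top rat dose, 1000 mg/kg/day, "with most conservative total AUC₂₄ (in male rats) of 210000 ng•h/mL". The mitigation column of the same row says "PK stopping total AUC₂₄ criterion set at ≥200-fold lower exposures" and refers the reader to Section 6.6.1.

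Section 6.6.1 sets the AUC24 limits at "18,400 ng•h/mL (in Part 1") and "3,680 ng•h/mL (in Part 2 with revision to this stopping limit to be considered" by amendment after a formal interim analysis). Section 4.3.2 gives their origin. The Part 1 limit is described as "reflecting 50% of exposure in males at the NOAEL dose (300 mg/kg/day) in the 6-week toxicity study in rats"; the Part 2 limit is 10% of the same exposure. Section 2.2.4 reports the rat NOAEL AUC24 as "36,800 (males) and 89,100 (females) ng•h/mL".

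Section 2.3 names Table 1 as the summary of potential risks. Among the ways those risks are reduced, it says that "the a priori identified PK stopping limits will not be exceeded".

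**The concern.** The toxic exposure, the claimed margin and the pointer to the limit all sit in one table row, and they do not agree. A limit 200-fold below 210,000 ng•h/mL would be 1,050 ng•h/mL, and no such limit appears in the documents. Both limits in force are well above it.

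The participants expect no clinical benefit. An ethics committee, regulator or investigator who takes the renal margin from Table 1 would believe the stopping limit keeps exposure much further from the observed kidney findings than it does. The error runs in the unsafe direction.

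**Working it through.** **Inputs (Protocol)**
- Male-rat AUC24 with renal findings: 210,000 ng•h/mL (Table 1, renal row).
- AUC24 limits: 18,400 (Part 1) and 3,680 (Part 2) ng•h/mL (Sections 4.3.2 and 6.6.1).
- NOAEL AUC24: male rat 36,800, female rat 89,100, monkey 88,500 ng•h/mL (Section 2.2.4).
- Fraction unbound: rat 0.422, human 0.382 (Section 2.2.2).
- QT row of Table 1: Cmax with QT effect 14,400 ng/mL, Cmax limit 1,450 ng/mL.

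**Step 1. Do the limits follow from their stated derivation?** 0.5 × 36,800 = 18,400 and 0.1 × 36,800 = 3,680. They do.

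**Step 2. Does the toxic-exposure-over-limit calculation work elsewhere in Table 1?** The QT row says "criterion set at close to 10-fold lower (1450 ng/mL"). 14,400/1,450 = 9.93, so that row is right.

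**Step 3. The same calculation for the renal row.**
- Part 1: 210,000/18,400 = 11.41.
- Part 2: 210,000/3,680 = 57.07.

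The stated figure of at least 200 is not reproduced.

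**Step 4. Other comparators, since the bullet names none.** Each entry is the comparator AUC24 divided by the limit.

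| Comparator | Part 1 | Part 2 |
|---|---|---|
| Male rat, renal findings, total | 11.4 | 57.1 |
| Male rat, renal findings, unbound: 210,000 × 0.422 / (limit × 0.382) | 12.6 | 63.0 |
| Male rat NOAEL (36,800) | 2.0 | 10.0 |
| Female rat NOAEL (89,100) | 4.8 | 24.2 |
| Monkey NOAEL (88,500) | 4.8 | 24.0 |

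The largest value is 63.0.

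**Step 5. Size of the overstatement.**
- Total exposure: 200/11.41 = 17.5 (Part 1) and 200/57.07 = 3.5 (Part 2).
- Unbound exposure: 200/12.61 = 15.9 and 200/63.04 = 3.2.

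**Step 6. What would have to be true for 200-fold to hold.**
- With the limits as stated, the toxic AUC24 would have to be at least 200 × 18,400 = 3,680,000 ng•h/mL for Part 1, or 200 × 3,680 = 736,000 for Part 2.
- With the toxic AUC24 as stated, the limit would have to be 210,000/200 = 1,050 ng•h/mL. This is arithmetic only, not a proposed limit.
- Projected AUC24 already exceeds 1,050 at 100 mg: 1,800 after a single dose (Table 3) and 2,300 after repeated dosing (Table 4).

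**The case against.** The strongest objection concerns weight. The operative limits are explicit, and they agree across Sections 4.3.2 and 6.6.1 and the notes to Tables 3 and 4. Section 9.5 and SAP Section 7.1 repeat the Part 2 limit. The derivation from the male-rat NOAEL is open, so a careful reader can see the true distances (2-fold and 10-fold to that NOAEL) without Table 1. No endpoint, analysis, sample size or stopping action depends on the 200-fold figure. All of this stands, and it limits the consequence of the error. It does not make the sentence correct.

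A second objection is that the QT row does not fix a convention for the whole table. The convulsions row lists a toxic Cmax of 46,000 ng/mL, which is 46,000/1,450 = 31.7 times the limit, yet describes the limit as one tenth of the NOAEL exposure. That is fair: the QT row does not prove what the renal row intended. But NOAEL comparators only shrink the renal margin.

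A third is that ratios above 200 can be formed from the documents. Against projected exposures at low doses, 210,000/180 = 1,167 for 10 mg single and 210,000/680 = 309 for 30 mg repeated. These describe a dose, however, and the bullet describes the stopping criterion.

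Two further explanations also fail:
- The female-rat AUC24 at 1000 mg/kg/day is not given, but the row itself chooses the male value as its most conservative figure.
- Text left over from before Amendment 1 does not explain 200 either. The document history calls the revised limits more conservative, so a higher earlier limit would have given a smaller margin. It also lists Table 1 among the places revised.

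A misread digit in the text extraction cannot be excluded, but nothing points to one.

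**Conclusion.** The concern holds. Against the exposure named in its own row, Table 1 overstates the renal margin of the AUC24 stopping criterion about 17.5 times for Part 1 (11.4-fold, not at least 200-fold) and 3.5 times for Part 2 (57.1-fold). Correcting for protein binding changes this little, to 12.6-fold and 63.0-fold.

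The conclusion assumes that the 210,000 ng•h/mL figure and the two limits are as printed. It does not depend on the choice of comparator among those the protocol gives, since none reaches 200. The margins also apply to group averages, because Section 6.6.1 tests average exposure; an individual with above-average exposure would have a smaller margin.

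This should be fixed, because it misstates a safety property of a decision threshold in the table on which the benefit/risk section relies. It does not show that the stopping rule itself is wrong.

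**What to change.** Reconcile the renal row of Table 1 with Sections 4.3.2 and 6.6.1. The row should state the margin separately for Part 1 and Part 2 and name the exposure it is measured against. With the limits now in force and 210,000 ng•h/mL as comparator, those margins are about 11-fold and about 57-fold. If the sponsor had another comparator in mind, it should be named and its value given. Which limit is appropriate is for the sponsor to settle, and no view is taken here.

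The cost is one line in Table 1. If the limits stay as they are, the stated renal margin becomes less favourable; no analysis or sample size changes.
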